8.1.1 Packaging and Formulation of Investigational Product

Talimogene laherparepvec will be presented as a sterile, semi-translucent to opaque solution for injection (opacity is different for each concentration) preservative-free frozen liquid in a single use 2 mL cyclic olefin polymer (COP) plastic resin vial. Each vial will contain talimogene laherparepvec at a nominal concentration of 10^6 PFU/mL or 10^8 PFU/mL in an aqueous sodium phosphate buffer with sodium

NCI Protocol #:

Version Date: March, 13, 2023

chloride, sorbitol and myo-inositol added as stabilizers and water for injection (WFI). Vials are appropriately filled to ensure that a sufficient deliverable dose is provided. Each 2 mL vial will contain approximately 1.15 mL of talimogene laherparepvec with a 1.0 mL deliverable volume. Each vial is intended for single use only and will be available in one of two different presentations:

Current supplies of talimogene laherparepvec is provided as a preservative-free solution in a single-use vial without a clear copolyester plastic sleeve. The product label is found on the vial itself.

Future supplies of talimogene laherparepvec will be provided as a preservative-free solution in a single-use vial permanently inserted into a clear copolyester plastic sleeve. The product label will be found on the vial sleeve

Note that the Closed System Transfer Device (CSTD) tested for use with the vial sleeve is the PhaSeal CSTD

Vials will be sealed with gray rubber stoppers, Fluoropolymer-coated on the product side. The vial caps will be color coded and may be used to help distinguish between the 10^6 PFU/mL and 10^8 PFU/mL vial concentrations. The supply for 10^6 PFU/mL vials will be packaged separately from the supply for the 10^8 PFU/mL vials.

- The 10^6 PFU/mL strength is supplied in a box containing 10 vials.
- The 10^8 PFU/mL strength is supplied in a box containing 20 vials.

The dimensions of the box (of both strengths) are approximately 12.7 x 12.7 x 5 cm (4.891 in. x 4.891 in. x 1.969 inches). Due to the temperature at which talimogene laherparepvec packaging occurs no tamper-evident seal or closure seal will appear on the boxes. Talimogene laherparepvec is sensitive to light and should be protected from light during storage.

8.1.2 Drug storage

To ensure stability and quality are maintained, the product must be stored correctly upon receipt and for the duration of the study under the conditions specified below.

Talimogene laherparepvec must be stored in a non-cycling freezer maintained at a set point of -80°C in a secured location until planned use. Cycling, frost-free, auto defrost freezers must not be used since they cycle to warmer temperatures several times a day. Vials should be kept within the secondary container to protect from light. [Table 3](#) outlines the storage temperature requirements.

Storage of Talimogene Laherparepvec - Freezer Set Point

| Freezer Set Point (°C) | Acceptable Variation | Acceptable Range |
|------------------------|----------------------|------------------|
| -80°C | ± 10°C | -90°C to -70°C |

Talimogene laherparepvec is stable if maintained in accordance with the guidelines described in this document and the provided expiration date.

To ensure GCP compliance with regards to the storage of biological products, talimogene laherparepvec should be segregated and stored on its own shelf in the freezer. Sites should also refer to local guidance on storing clinical trial drugs.

8.1.3 Agent Ordering and Agent Accountability

Sponsors of clinical studies are required to establish a record of receipt, storage, use and disposition of all talimogene laherparepvec used to conduct a clinical study. The Sponsor of the clinical study is responsible for ensuring that accountability is maintained and accurate at each clinical site where the study is conducted. At study activation or as required, initial shipments of talimogene laherparepvec 10⁶ PFU/mL and 10⁸ PFU/mL concentrations will be shipped to the contact and address provided by the Study Sponsor. It is the responsibility of the Study Sponsor to maintain the records of talimogene laherparepvec accountability in accordance with ICH GCP.

Complete study drug information (including packaging, labeling, ordering, storage and disposition) is provided in the Talimogene laherparepvec Pharmacy Information Guide.

9. CORRELATIVE, AND SPECIAL STUDIES

The underlying hypothesis driving this clinical trial is that the induction of high titers of antibody by intra-tumoral talimogene laherparepvec will result in enhanced tumor recognition by the immune system, and subsequently leading to improved disease control. Patients treated on this study will undergo evaluation of immune response to treatment, including serologic response, and evaluation of the baseline and post-treatment cytokine profile and inflammatory response.

The results will be used to correlate response to vaccination with subsequent clinical outcome.

Blood Samples:

Patient serologic and inflammatory response will be measured at baseline during Screening or prior to the Visit Week 1 injection of the study drug, and immediately preceding injections at Visit Weeks 4, 8, 12 or 13

With each collection, 1 Red top tube and 1 pink top tube for serum and mononuclear cells (MNC) will be collected for the following tests:

- Cytokine Profile: IL-1 β , IL-2, IL-4, IL-6, IL-8, IL-10, IL-12, TNF-alpha, IFN-gamma, IFN-alpha, GM-CSF.
- NK-cell functional assay.

Tumor Tissue Samples:

The tumor biopsy samples will be used to study the relationship between the immune response induced by talimogene laherparepvec and clinical response or resistance to talimogene laherparepvec. Tumor slides will be systemically analyzed at baseline and post-treatment to evaluate changes in the number and/or type of immune cells infiltrating the tumor during treatment. The protocol may be modified to include analysis of the immune and cancer cells in the tumor to identify ribonucleic acid transcripts and/or proteins whose levels change with treatment, and to assess tumor specific mutations or epigenetic changes.

- The biopsy sample will be assessed for baseline tumor infiltrating lymphocytes (TILs) by the same pathologist. This will include CD3, CD4, CD8, CD56, and FOXP3 positive cells.
- Post treatment TILs, as above, will be assessed on the resected tumor at the end of treatment.
- Optional pre- treatment tumor biopsies will be taken from approximately 5 subjects total and immune markers will be compared between pre and post treatment tissue in the immunology lab

Additionally, blood samples and tumor samples may be saved for any potential additional or future analyses such as tumor specific mutations or epigenetic changes (eg, somatic mutations) on tumor tissues.

The study may be amended to include additional testing to ensure analytical methods produce reliable and valid data throughout the course of the study. This can also include, but is not limited to, investigation of unexpected results, incurred sample reanalysis, and analyses for method transfer and comparability.

10. STUDY CALENDAR

10.1 Study Procedures

| Study Procedures | Screening | Study Treatment (week number) ^a | | | | | | | | | | | | | | Safety follow up (30 days post last TVEC) | Long-term follow up ^h |
|---|--|--|---|---|----------------|---|---|----------------|---|---|-----------------|----|--|---------------------|--|---|----------------------------------|
| | | 1 ⁱ | 2 | 3 | 4 ⁱ | 5 | 6 | 7 ⁱ | 8 | 9 | 10 ⁱ | 11 | 12 (End of treatment ⁱ) | Surgery (wks 12-14) | | | |
| General Assessments | | | | | | | | | | | | | | | | | |
| Progress Note | X | X | | | X | X | X | X | X | X | X | X | X | | | X | |
| Optional tumor biopsy ^k | X | | | | | | | | | | | | | | | | |
| Recording of Concomitant Medications | X | X | | | X | X | X | X | X | X | X | X | X | | | X | |
| Vital Signs ^b | X | X | | | X | X | X | X | X | X | X | X | X | | | X | |
| Physical Exam, including weight | X | X | | | X | X | X | X | X | X | X | X | X | | | X | |
| ECG | X | | | | | | | | | | | | | | | | |
| ECOG Performance Status | X | | | | | | | | | | | | | | | | |
| Review of AEs & SAEs ^c | | X | | | X | X | X | X | X | X | X | X | X | | | X | |
| Talimogene laherparepvec injection ^j | | X | | | X | X | X | X | X | X | X | X | X | | | | |
| Correlative labs ⁱ | | X | | | X | | | | X | | | | X | | | | |
| Radiation | | | | | X | X | X | X | X | | | | | | | | |
| Survival Status/Disease Recurrence | | | | | | | | | | | | | | | | | X |
| Local Laboratory Tests^d | | | | | | | | | | | | | | | | | |
| Pregnancy (serum or urine) | X | | | | | | | | | | | | | | | X | |
| CMP ^d | X | X | | | X | X | X | X | X | X | X | X | X | | | X | |
| CBC, differential, Platelets ^d | X | X | | | X | X | X | X | X | X | X | X | X | | | X | |
| Coagulation (PT or INR and PTT or aPTT) | X | | | | | | | | | | | | | | | | |
| AST, ALT, AlkPhos, Bili, Albumin ^d | X | X | | | X | X | X | X | X | X | X | X | X | | | X | |
| TSH, free T3, T4 | X | | | | | | | | | | | | | | | | |
| Clinical & Radiographic Tumor/Response Assessments | | | | | | | | | | | | | | | | | |
| Tumor biopsy | Must be biopsy confirmed within 3 months prior to study enrollment | | | | | | | | | | | | | | | | |
| Primary Tumor Assessment (MRI/CT) ^{e,g} | X | | | | | | | | | | | | X | | | | |
| CT Chest, Abdomen, | X | | | | | | | | | | | | X | | | | |

| | | | | | | | | | | | |
|---------------------|--|--|--|--|--|--|--|--|--|--|--|
| Pelvis ^f | | | | | | | | | | | |
|---------------------|--|--|--|--|--|--|--|--|--|--|--|

- a. Assessments will occur on Day 1 (+/- 3 days) of the week number.
- b. Blood pressure, resting pulse, respiration rate, and temperature.
- c. All serious adverse events (SAEs) will be reported within 24 hours of the discovery of the event.
- d. May be monitored more frequently if indicated.
- e. Tumor assessment will be documented per RECIST.
- f. CT chest, abdomen, and pelvis at screening (up to 28 days prior to initiation of treatment) and Week 12 (End of treatment)
- g. Primary tumor (MRI/CT) at screening (up to 28 days prior to initiation of treatment)) and on Day 1 week 12 (\pm 2 weeks). Simulation scans done for radiation planning are acceptable
- h. Follow up per standard of care (approximately every 12-16 weeks), at the discretion of the treating physician and as per NCCN guidelines. Data for survival status and disease recurrence only will be collected through chart review.
- i. Correlative labs for serologic and inflammatory response; 1 Marble Red top and 1 Pink top . See Section 9 (+/- 7 days).
- j. Talimogene laherparepvec will be given weeks 1 through 12 (+/- 2 weeks) when surgery is expected to be performed. The injections must be given the same day of the week +/- 3 days.
- k. Optional tumor biopsy can be done anytime before week 1 dosing

10.2 Screening Procedures:

- Procedures to be completed within 28 days of enrollment/randomization and prior to first treatment (unless otherwise noted).
 - Informed Consent
 - Review of eligibility criteria
 - Recording of medical history and concomitant medications
 - Physical Exam (including weight)
 - ECG
 - Vital Signs (Blood pressure, resting pulse, respiratory rate, temp.)
 - Radiographic imaging (Chest, abdomen, and pelvis and all other sites of disease)
 - Imaging of primary tumor site
- Laboratory Assessments
 - Within 28 days of enrollment and prior to first treatment.
 - HIV test: Required if clinically indicated
 - Hepatitis B and/or C tests: Required if clinically indicated
 - \leq 10 days of enrollment
 - Hematology panel (with 5 part differential). 3 part differential if 5 part unable to be performed.
 - Chemistry panel
 - Coagulation panel
 - Thyroid function tests
 - \leq 3 days of enrollment
 - Serum or urine pregnancy test for females of childbearing potential

10.3 Long-term Follow up

After the end of treatment visit is completed, subjects will be followed according to standard of care (approximately every 12 weeks), at the discretion of the treating physician, at which time disease recurrence and survival status will be assessed for up to 5 years. Data for disease recurrence and survival status only will be collected per chart review, phone call or email.

11. MEASUREMENT OF EFFECT

11.1 Pathologic Response

At the end of the neoadjuvant therapy, patients will undergo resection of the treated tumor. The pretreatment biopsy and all the resected tumor samples must be reviewed by the same pathologist.

- The percentage of post treatment tumor necrosis must be documented. The primary end point for this study is pathologic complete response (pCR) and is defined as $\geq 90\%$ tumor necrosis following concurrent radiation therapy and talimogene laherparepvec.
- Additional immunohistochemical studies will be performed as described in Section 9.

11.2 Time to Disease progression (TTP)

TTP is defined as the time from Enrollment until objective tumor progression including local and distant recurrences.

11.3 Other Response Parameters

The following response assessment guidelines may be amended during the course of the study if changes are made to the current RECIST Guidelines or if a new disease assessment tool becomes available.

Response Measurement Criteria:

- Measurements of the tumor in its largest dimension should be obtained at baseline and at the end of the treatment phase, prior to surgical resection.
- Response criteria should be by RECIST.
 - Complete response is the disappearance of all target lesions.
 - Partial response is a 30% decrease in the sum of the longest dimensions of the target lesions, relative to baseline.
 - Progressive disease is an increase of 20% or more in the sum of the longest dimension of target lesions
 - Stable disease is a decrease in the tumor size of $< 30\%$ or an increase of $< 20\%$.
- Antitumor response by pathologic assessment will be performed on the resected tumors.
- Pathologic assessment will be performed per institutional guidelines.
 - The percent of tumor necrosis and the percent of tumor-infiltrating lymphocytes will be documented.
 - Complete pathological response will be considered $\geq 90\%$ pathologic tumor necrosis.

Radiologic response will be evaluated in this study using the new international criteria proposed by the revised Response Evaluation Criteria in Solid Tumors (RECIST) guideline (version 1.1) [Eur J Ca 45:228-247, 2009]. Changes in the largest diameter (unidimensional measurement) of the tumor lesions and the shortest diameter in the case of malignant lymph nodes are used in the

RECIST criteria.

Please see Appendix B for more details of the RECIST Guidelines.

12. STATISTICAL CONSIDERATIONS

12.1 Study Design/Endpoints

Phase Ib

| Number of Patients with DLT at a Given Talimogene Laherparepvec Dose | Decision Rule |
|--|---|
| ≥ 2 | Dose level will be declared toxic. If this is the lowest dose level, stop the study due to excessive toxicity; otherwise enter three additional patients at the next lowest dose level. |
| ≤ 1 out of 3 | Enter three more patients at this dose level. |
| ≤ 1 out of 6 | This is the recommended Phase II dose. |

Up to 6 patients will be treated at each dose level. The recommended Phase II dose will be defined as the highest dose level for which at most 1 out of 6 patients experience a DLT.

Phase II

The primary objective of the Phase II portion of this study is to evaluate the preliminary evidence of anti-tumor activity of talimogene laherparepvec in combination with external beam radiation therapy. The primary endpoint of interest is pathologic complete response (pCR) rate defined as the proportion of subjects with pathologic tumor necrosis of $\geq 90\%$. Estimates of historic pCR based on tumor necrosis $\geq 90\%$ for the treatment of soft tissue sarcomas with external beam radiation therapy are not available in the current literature. However, a pCR rate of 30% would be considered unacceptable for the proposed combination treatment whereas a pCR of 55% or more is considered clinically important. Sample size requirements are based on an optimal Simon two-stage design with 80% power and a significance level of 5%. Nine (9) patients will

be enrolled in the first stage, and the study will be terminated if 3 or fewer respond. Otherwise, an additional 26 patients will be enrolled in the second stage. If 15 or more of the 34 total patients respond, the treatment will be deemed worthy of further investigation. This design has an expected sample size of 16.0 and a 0.73 probability of early termination.

Data Analysis and Reporting

The number and severity of all adverse events will be summarized by simple descriptive statistics. pCR and ORR (CR+PR) rate point estimates and 95% exact confidence intervals will be reported. For TTP (time from first day of study treatment to first documented disease progression) and OS (time from first day of study treatment to death due to any cause), survival curves using the Kaplan-Meier method will be constructed. Estimates along with 95% confidence intervals will be reported.

REFERENCES

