APPENDIX E: DATA AND SAFETY MONITORING PLAN

Type of Clinical Trial:

| | |
|--|--|
|  Investigator-initiated (UI/HCCC) | Investigator-initiated, participating site |
| Pilot study | Phase I |
|  Phase I/II | Phase II |
| Phase III | Compassionate-use/Expanded Access |
|  Interventional Treatment | Interventional Non-Treatment |
| Non-Interventional | |

Study risk-level:

Level 1—low risk of morbidity or death, * <1% of death or any adverse event

Level 2—risk of death* <1% or any adverse event 1% – 5%

Level 3—risk of death* 1% – 5% or grade 4 – 5 SAE 1% – 5%

Level 4—risk of death* >5% or grade 4 – 5 SAE >5%
Drugs being used on a “compassionate” basis

* *Risk of death* refers specifically to 100-day treatment-related mortality

Reporting and Monitoring Requirements:

All institutional investigator initiated trials (IITs), regardless of assigned risk level are subject to routine DSMC monitoring activities which may include but are not limited to review of signed consent documents, eligibility and adverse event reporting.

All institutional IITs have the following **reporting requirements** as part of their DSMP:

- Register all subjects in HCCC's Clinical Trial Management System, OnCore
- Document Adverse Events
- Document protocol deviations
- Provide an annual progress report to the DSMC via OnCore data export

Selected monitoring strategy based on risk-level:

Risk Level 4

Interventional treatment trials involving investigational agents or devices with a risk of death* (>5% or grade 4 – 5 SAE >5%), e.g. all investigator initiated INDs, most Phase I/II

trials, gene therapy, gene manipulation or viral vector systems high-risk clinical procedures if performed solely for research purposes. The use of a new chemical or drug for which there is limited or no available safety data in humans.

Study Safety Review

An independent study monitor and/or the DSMC Chair (or designee), will review study data (provided by the PI/available in OnCore) and communicate with the PI at least biannually. A copy of this communication will be forwarded to the DSMC and PRMC Chairs.

Additional Reporting Requirements:

- A scanned copy of the completed eligibility checklist, with screening information and PI signature, will be attached in OnCore for ongoing review by DSMC staff.

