- Serious adverse events will be entered directly into an OnCore SAE report by the research team. OnCore will send an automatic notification to the DSMC Chair/acting Chair and staff for review.
- The DSMC utilizes a risk-based monitoring approach. The trial's research records will be monitored at minimum twice per year. Monitoring may be done more frequently depending on the protocol, risks to subjects, reported serious/adverse events, patient population and accrual rate. Records for a minimum of 25% of subjects will be monitored for the entire study.

Monitoring will involve the following:

- review eligibility of patients accrued to the study,
- check for the presence of a signed informed consent,
- determine compliance with protocol's study plan,
- determine whether SAEs are being appropriately reported to internal and external regulatory agencies,
- compare accuracy of data in the research record with the primary source documents,
- review investigational drug processing and documentation,
- assess cumulative AE/SAE reports for trends and compare to study stopping rules.

- **Routine Adverse Event Reporting**

For non-serious Adverse Events, documentation must begin from the time the subject signs the informed consent document and continue through the 30-day follow-up period after the last dose of study drug.

Collected information should be recorded in the electronic/Case Report Forms (eCRF/CRF) for that subject. A description of the event, its severity or toxicity grade (according to [NCI's Common Toxicity Criteria \(CTCAE\)](#)), onset and resolved dates (if applicable), and the relationship to the study drug should be included. Documentation should occur in real time. The principal investigator has final responsibility for determining the attribution of the event as it is related to the study drug.

-
- **Serious Adverse Event Reporting**

For any experience or condition that meets the definition of a serious adverse event (SAE), recording of the event must begin after signing of the informed consent and continue through the 30 day follow-up period after treatment is discontinued.

Investigators must report to the DSMC any serious adverse events (SAE), whether or not they are considered related to the investigational agent(s)/intervention (21 CFR 312.64). SAEs must be reported via an OnCore SAE Report within 24 hours of learning of the event.

An adverse event is considered **serious** if it results in ANY of the following outcomes:

1. Death

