- **Allergic Reaction:** As with any medication, you may have an allergic reaction to talimogene laherparepvec. Symptoms of an allergic reaction in general may include headache, rash, itching, flushing, swelling, shortness of breath, nausea and sometimes vomiting. Severe allergic reactions can cause dizziness, severe skin reactions, difficulty breathing or swallowing, a decrease in blood pressure, and could be life threatening. If you have symptoms of an allergic reaction, you should contact the study doctor or his/her study staff immediately. If you have had an allergic reaction to talimogene laherparepvec or any of its ingredients, you should inform your doctor.
- **Autoimmune Reactions:** Autoimmune reactions to the body's own tissues have been reported in some patients administered talimogene laherparepvec. Examples of autoimmune reactions that have been reported in patients receiving talimogene laherparepvec include inflammation of the kidneys (nephritis), blood vessels (vasculitis), lungs (pneumonitis) and worsening psoriasis. It is possible that an autoimmune reaction could occur in any part of the body. Please tell your doctor if you have had any type of autoimmune disease before treatment with talimogene laherparepvec, and all treatments you are receiving for the disease.

Stopping Rules:

As a phase II study, stopping rules do not apply. If a subject dies during active study treatment:

- Trial will be placed on accrual hold until case review
- The death will be reviewed by the principal investigator, IND medical monitor, and IND sponsor (and, as applicable, treating physician)
- Adverse events, including deaths on study, will be reviewed at IND investigators' meeting.
-
-

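### In Phase II no count of non-fatal DLTs triggers an accrual pause or an unscheduled trial-level review

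*Combined protocol and SAP*

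**What the plan says.** **Phase Ib.** Section 12.1 treats up to 6 patients per dose level. Two or more DLTs make a level toxic, and the recommended dose is the "highest dose level for which at most 1 out of 6 patients experience a DLT". Section 5.1 gives the same rule.

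**Phase II.** The only decision rule in Section 12.1 counts pathologic responders: nine patients will "be enrolled in the first stage, and the study will be terminated if 3 or fewer respond". Adverse events are summarized descriptively. Under Stopping Rules, Appendix E says "As a phase II study, stopping rules do not apply". It then names one trigger, a death during active study treatment, with the consequence "Trial will be placed on accrual hold until case review".

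**Individual patients.** Sections 5.6 and 6.1 to 6.3 deal with a DLT by delaying, spacing out or discontinuing that patient's injections.

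**Oversight that does exist.** Under Appendix E, an independent monitor and/or the DSMC Chair reviews study data and must "communicate with the PI at least biannually". Research records are monitored at least twice a year, and monitors must "assess cumulative AE/SAE reports for trends and compare to study stopping rules". For serious events, "SAEs must be reported via an OnCore SAE Report within 24 hours of learning of the event". In addition, "Adverse events, including deaths on study, will be reviewed at IND" investigators' meetings.

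**The concern.** Monitors are told to compare cumulative events with study stopping rules, yet the same appendix says that none apply in Phase II. For non-fatal toxicity there is nothing to compare with. If DLTs accumulate, the plan does not say how many would oblige anyone to pause accrual or call a review outside the schedule.

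This matters because Phase Ib is small and the exposure is new. Sections 1.2.1 and 5.2.1 show a maximum of 8.0 mL per treatment at the higher concentration, against 4 mL in the predecessor sarcoma trial. Section 7.4 asks for very close monitoring of impaired wound healing when radiation is given concurrently. A moderately high DLT rate could pass six patients and show itself only in Phase II. The gap is widest if the treatment works, because the response rule then seldom stops the trial.

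**Working it through.** **Inputs.** From Section 12.1: pass a dose with at most 1 DLT in 6; stop for futility with 3 or fewer responders in 9; 26 more patients in stage 2; pCR rates of 30% and 55%. The Phase II total is 28 in Section 5.1, 34 in Section 12.1, and 9 + 26 = 35 by addition, so both ends are shown. The plan states no target DLT rate; every DLT rate p below is an assumption.

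**The plan's own figures.** P(at most 3 of 9 respond) is 0.730 at pCR 30%. Expected enrolment is 9 + 0.270 × 26 = 16.0. Both match the stated 0.73 and 16.0. At pCR 55% the futility rule stops only 0.166 of the time, and expected enrolment is 9 + 0.834 × 26 = 30.7.

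**Phase Ib.** P(pass) = P(0 of 3) × P(at most 1 of 3) + P(1 of 3) × P(0 of 3) = (1 − p)^6 + 6p(1 − p)^5. At p = 30%: 0.118 + 0.303 = 0.42.

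**Example Phase II trigger.** Pause at 4 or more DLTs in 9, or 6 or more in 18; a third look pauses at 8 or more in 27. Exact sequential binomial, without the futility stop:

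| True DLT rate | Phase Ib passes | Pause, two looks | Pause, three looks |
|---|---|---|---|
| 10% | 0.89 | 0.01 | 0.01 |
| 1/6 | 0.74 | 0.09 | 0.11 |
| 20% | 0.66 | 0.16 | 0.22 |
| 25% | 0.53 | 0.32 | 0.43 |
| 30% | 0.42 | 0.50 | 0.65 |
| 40% | 0.23 | 0.81 | 0.92 |

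At 30% the three looks contribute 0.270, 0.232 and 0.148, which sum to 0.650.

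**Both rules together.** Assume that DLT and response are independent and that a pause ends accrual. With S the chance of a futility stop, total 35, three looks and p = 30%, expected enrolment is

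9 × (0.270 + 0.730 × S) + (1 − S) × (18 × 0.232 + 27 × 0.148 + 35 × 0.350).

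This gives 12.7 for S = 0.730 (pCR 30%) and 20.6 for S = 0.166 (pCR 55%). DLTs averted = 0.30 × the fall in expected enrolment:

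| Phase II total, looks | pCR | Expected enrolment | DLTs averted if Phase Ib passed the dose | × 0.42, per trial started |
|---|---|---|---|---|
| 35, three | 30% | 16.0 to 12.7 | 1.0 | 0.4 |
| 35, three | 55% | 30.7 to 20.6 | 3.0 | 1.3 |
| 28, two | 30% | 14.1 to 12.1 | 0.6 | 0.25 |
| 28, two | 55% | 24.8 to 18.6 | 1.9 | 0.8 |

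At a DLT rate of 1/6, at most 0.3 DLTs are averted even with a total of 35 and Phase Ib already passed.

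**Evidence for a low rate.** Section 1.2.1 reports no DLTs in the predecessor trial (30 enrolled, 4 mL) and none among 17 head and neck patients. If all were evaluable, the one-sided 95% upper bounds are 1 − 0.05^(1/30) = 9.5% and 1 − 0.05^(1/17) = 16.2%. Neither group received up to 8 mL weekly with radiation for sarcoma.

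**The case against.** A reader might infer that Phase II has no trial-level safety review. The documents do not support that. The twice-yearly review and monitoring, the 24-hour SAE reports and the review at IND investigators' meetings are obligations, whatever the count. Looks every 9 patients would come more often than twice a year only if accrual exceeded 18 a year, and the plan gives no accrual rate. What stands is narrower: none of these mechanisms has a threshold or obliges a pause.

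A reader might also infer that four of the nine full-dose injections (weeks 9 to 12 of weeks 4 to 12) lie outside the DLT window. Section 6.2 covers the time during treatment and through week 8, which can be read as ending at week 8 or as covering all treatment. The point does not depend on which is right.

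The objection that Section 6.2 would miss the wound events of most interest is sound. Outside the immune-mediated, allergic and plasmacytoma categories it counts only unexpected toxicity of grade 3 or higher, while Section 5.2.4 expects wound complications of any grade in about one third of patients. A trigger limited to Section 6.2 events through week 8 would not address that risk, so the count needs widening.

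Finally, the benefit is modest. It requires a toxic dose to have passed Phase Ib, and no data in the documents point to a rate of 25% to 40%. The example rule is also not sensitive: at 30% it misses 50% of cases with two looks and 35% with three.

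**Conclusion.** The point holds in this form: in Phase II no count of non-fatal DLTs triggers an accrual pause or an unscheduled trial-level review, and Appendix E refers its monitors to stopping rules that it says do not apply. It does not follow that 8 mL is unsafe. Appendix D's remark that the maximum safe dose is undetermined is general product information, and the reported experience at lower or different doses shows no DLTs.

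At an assumed 30% DLT rate, the example trigger averts up to 1.0 DLT (pCR 30%) or 3.0 (pCR 55%) with a total of 35, and 0.6 or 1.9 with a total of 28, given that Phase Ib passed the dose. Multiplied by the 0.42 chance of passing, these become 0.4 or 1.3, and 0.25 or 0.8. They are upper bounds, because they assume that review ends accrual and that nobody enrols while a look matures. They apply to Section 6.2 events at one constant rate and would change with a wider count. The change is a cheap improvement and worth making.

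**What to change.** In Section 12.1 (Phase II), add a count that pauses accrual for review by the existing DSMC. For example: 4 or more of 9 at the stage-1 interim and 6 or more of 18, with 8 or more of 27 only if Phase II enrols 34 or 35. With a total of 28, a look at 27 protects at most one patient. The sponsor should set the boundary from the DLT rate it would not accept.

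Count Section 6.2 events from first dose to last injection. Also count related wound events of grade 3 or higher reported up to 30 days after the last dose, with a boundary that allows for the expected radiation wound rate. The example bounds should not be carried over to that wider count unadjusted. In Appendix E, replace the sentence that stopping rules do not apply with a reference to this trigger, and keep the death hold. The response rule and individual dosing rules stay as they are.

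The cost is a short amendment, with no new committee, patients or procedures. Adverse events are already graded, attributed and collected to 30 days after the last dose. Section 7.1 exempts non-serious events of an expected post-operative course unless attributable to study drug, so attribution will decide which wound events are counted.

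The downside is an unnecessary temporary pause, with probability about 0.01 at a true rate of 10% and 0.09 to 0.11 at 1/6. Some patients may enrol while the second look matures: if four do so with a total of 28, the DLTs averted at 30% fall from 0.6 and 1.9 to 0.5 and 1.6. The first look has no such overrun if accrual waits for stage-1 pathology, which Section 12.1 does not state.
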